#### 4.6.7 Percent of time spent with blood glucose values at various cut points

Subjects in Cohort 2 of Study VC-02-101 are required to wear their CGM, at minimum, during the 30-day period prior to their scheduled clinic visits, although wearing of the CGM for the entire two-year study is encouraged. The cut points of <54 mg/dL,  $\ge54 \text{ to } <70 \text{ mg/dL}$ ,  $\ge70 \text{ mg/dL}$  to  $\le180 \text{ mg/dL}$ , >180 mg/dL, and >250 mg/dL will be assessed. Also, severe HEs characterized by an altered mental and/or physical status requiring assistance will be summarized.

The summarization will be performed three ways: over the entire 24-hour time period, over the nocturnal (CGM value below/above the cut point occurs between 12 a.m. - 6 a.m.) time period, and over the daytime (CGM value below/above the cut point occurs between 12 a.m. - 6 a.m.) time period.

Baseline CGM data will be utilized to calculate percentages spent with blood glucose values at the various cut points for up to 28 days, starting at Day -3 (i.e., the day prior to immunosuppression induction) and working backwards for up to 28 days (through Day -30). For instances in which the available pre-implant dataset provides <28 days of data, the dataset will be supplemented with post-implant data, using data from Day 4 forward until 28 days of data is available. Data should not be used if an MMTT or SOGCT was performed on that day. In addition, the CGM data from the 14 days prior to each scheduled clinic visit will be used to calculate percentages spent with blood glucose values at the various cut points for these visits.

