## 4.6.3 Frequency of hypoglycemic events using subject-reported diary data

HE data collected on the "Hypoglycemic Event" eCRF page will be used collectively for HE data summary and analysis. These data are collected from the subject-completed diaries. Hypoglycemic event logs will be completed via subject diary (via provisioned phones) by subjects. Investigators will review the hypoglycemic event logs completed by the subjects at each study visit. Blank values in the hypoglycemic events (HEs) log are considered to be 0 values.

HEs will be classified in six ways: total HEs, severe HEs, nocturnal HEs, severe nocturnal HEs, daytime HEs, and severe daytime HEs. Total HEs are HEs that occur at any time during the 24-hour period. Severe HEs (SHEs) are HEs requiring the aid of another person to administer carbohydrates, glucagon, or other resuscitative assistance any time during the 24-hour period.

Nocturnal HEs are HEs that start during the 12 a.m. - 6 a.m. period. Severe nocturnal HEs are SHEs that start during the 12 a.m. - 6 a.m. period. Daytime HEs are HEs that start during the 6 a.m. to 12 a.m. period. Severe daytime HEs are SHEs that start during the 6 a.m. to 12 a.m. period.

The baseline average weekly frequency of subject-reported HEs, SHEs, nocturnal HEs, severe nocturnal HEs, daytime HEs and severe daytime HEs will be calculated using up to 28 days of data. The baseline average weekly frequency will be calculated using data starting at Day -3 (i.e., the day prior to immunosuppression induction) and working backwards for up to 28 days (through Day -30). For instances in which the available pre-implant dataset provides <28 days of data, the dataset will be supplemented with post-implant data, using data from Day 4 forward until 28 days of data is available. Data from days on which an MMTT or SOGCT was performed will not be used in the calculation.

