## 4.6.4 Frequency of hypoglycemic events using CGM data

CGM will also be utilized, based on the below specified rules, to evaluate the number of hypoglycemic episodes (number of times blood glucose falls below 70 mg/dL) and the number of severe hypoglycemic events (number of times blood glucose falls below 54 mg/dL) for each subject:

- A set of CGM readings < 70 mg/dL or <54 mg/dL, with a minimum overall duration of 15 minutes
- Up to two consecutive readings >= 70 mg/dL (or >= 54 mg/dL for separate summary) are allowed within the same episode
- If a subsequent episode starts within 60 minutes of the start of the previous episode, then they are combined and counted only as one episode

The total number (over the entire 24-hour time period) of episodes will be calculated as well as the number of nocturnal (starts during the 12 a.m. - 6 a.m. period) episodes and the number of daytime (starts during the 6 a.m. to 12 a.m.) episodes.

Baseline CGM-reported HE data will be calculated using up to 28 days of data. Baseline CGM-reported HEs will be recorded starting at Day -3 (i.e., the day prior to immunosuppression induction) and working backwards for up to 28 days (through Day -30). For instances in which the available pre-implant dataset provides <28 days of data, the dataset will be supplemented with post-implant data, using data from Day 4 forward until 28 days of data is available. Data from days on which an MMTT or SOGCT was performed, will not be included in the calculation. These

data will be used to calculate the baseline number of weekly total episodes, weekly nocturnal episodes, and weekly daytime episodes. In addition, the CGM data from the 14 days prior to each scheduled clinic visit will be used to calculate the number of weekly total episodes, the number of weekly nocturnal episodes, and the number of weekly daytime episodes for each of these visits. Data should not be used if an MMTT or SOGCT was performed on that day.

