## 6.2 Secondary Efficacy Endpoints and Analyses

Each of the secondary efficacy endpoints will be analyzed using an  $\alpha = 0.05$  level of significance. Given the large number of secondary efficacy endpoints, the p-values for these endpoints will be considered descriptive.

For all secondary efficacy analyses, the FAS (Cohort 2 subjects who meet the FAS criteria) will be used. Change from baseline in C-peptide AUC0-4h following an MMTT at Weeks 52, 78, and 104 and change from baseline in C-peptide AUC0-2h following an MMTT at Weeks 8, 12, 16, 20, 39, 52, 65, 78, 91, and 104 will be analyzed in a similar manner to the ANCOVA performed for change from baseline in C-peptide AUC0-4h at Week 26, with the relevant baseline as the covariate. For subjects who continue to have a C-peptide  $\leq 0.1$  ng/mL as determined by the simplified oral glucose challenge test, the AUC of the respective 2-hour MMTT will be set to 0. A listing of the 2-hr MMTT/C-Peptide and Glucose results will be provided, as well as a listing of the simplified oral glucose challenge.

Time to onset of biological response of C-peptide following MMTT will be assessed using Kaplan-Meier (KM) product-limit method, with the p-value from the logrank test also provided.

The number and percent of subjects achieving a positive stimulated C-peptide (defined as > 0.2 ng/mL) after implant will be analyzed using Fisher's exact test. The number and percent of subjects in each treatment group and the p-value from the Fisher's test will be provided (at each time point, where appropriate).

Change from baseline in frequency of hypoglycemic events (24-hour; daytime [start between 6 a.m. -12 a.m.]; nocturnal [start between 12 a.m. -6 a.m.]) at Weeks 16, 26, 52, 78 will be analyzed using ANCOVA, with treatment group as a factor and the relevant baseline as a covariate. This analysis will be performed using HEs from both the patient-reported diary and from CGM. A listing of hypoglycemic events will be provided for both patient-reported data and from CGM data.

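### SAP 4.6.7 defines the daytime CGM period with the nocturnal hours, so the daytime percent-time summary would duplicate the night-time one

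*SAP*

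**What the plan says.** SAP 4.6.7 derives the percentage of time at five CGM cut points: <54, ≥54 to <70, ≥70 to ≤180, >180 and >250 mg/dL. It sets out the periods as follows.

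- 24-hour: "The summarization will be performed three ways: over the entire 24-hour time period".
- Nocturnal: "over the nocturnal (CGM value below/above the cut point occurs between 12 a.m. - 6 a.m.) time period".
- Daytime: "and over the daytime (CGM value below/above the cut point occurs between 12 a.m. - 6 a.m".

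The nocturnal and daytime parentheses are identical. The text is intact at this point, with no redaction or broken table to explain it, and it belongs to the body of the SAP, not to the revision table.

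The other definitions of daytime agree with one another.

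- SAP 4.6.3, for diary-reported events: "Daytime HEs are HEs that start during the 6 a.m. to 12 a.m. period".
- SAP 4.6.4, for episodes derived from CGM: "daytime (starts during the 6 a.m. to 12 a.m.) episodes".
- SAP 6.2, for the analysis of event frequency: "daytime [start between 6 a.m. -12 a.m.]; nocturnal [start between 12 a.m. -6 a.m".
- Protocol 10.4.5.1 gives the same hours as SAP 6.2.

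**The concern.** Section 4.6.7 is a derivation rule, the kind of text from which a programming specification is written. The other daytime definitions concern when a hypoglycaemic event or episode starts. None of them formally governs percent time at the cut points. SAP 6.2, which plans the percent-time summary, does not restate any clock hours, so nothing later in the plan corrects the slip.

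At stake is a daytime table that is labelled as such but holds night-time data. Percent time at the CGM cut points is a listed secondary efficacy endpoint, and the SAP itself chose to split it by day and night. A reader comparing the two sub-periods would see identical values and no information specific to waking hours.

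**Working it through.** The plan gives no figure to reproduce. The check compares clock hours as sets, using the definitions quoted above.

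| Quantity | SAP 4.6.7 as written | Daytime as in SAP 4.6.3, 4.6.4, 6.2 and protocol 10.4.5.1 |
|---|---|---|
| Nocturnal | 0:00-6:00, 6 h | 0:00-6:00, 6 h |
| Daytime | 0:00-6:00, 6 h | 6:00-24:00, 18 h |
| Overlap of the two | 6 h (complete) | 0 h |
| Hours in neither | 24 − 6 = 18 h | 24 − (6 + 18) = 0 h |

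1. **Share of the day in neither sub-period, as written:** 18/24 = 75%.
2. **Per visit:** SAP 4.6.7 uses the 14 days before each scheduled clinic visit. With complete wear and no day excluded, the daytime summary would rest on 14 × 6 = 84 hours instead of 14 × 18 = 252 hours, one third of the intended amount. All 84 hours would be those already used for the nocturnal summary.
3. **Scope:** the periods are defined once for the whole section. The duplication therefore covers all five cut points, at baseline and at each visit, and so also any change from baseline by sub-period.
4. **What the error does to a value (illustrative figures, not from the documents):** suppose time in range is 60% at night and 70% by day. The 24-hour value is (6 × 60 + 18 × 70)/24 = 67.5%. The daytime column as written would show 60%, where the 6 a.m. to midnight window gives 70%. With 70% at night and 60% by day, the 24-hour value is 62.5% and the daytime column would show 70%. The error can run in either direction and vanishes only when night and day are equal.

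**The case against.** The strongest case against is that this is a clerical slip with an obvious remedy.

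- **The intent is plain.** Four other places agree on the hours, one of them also for CGM data, and a daytime period listed separately from a nocturnal one cannot sensibly mean midnight to 6 a.m. This stands.
- **Validation might catch it.** SAP 4.1 has programs developed and validated by different people, and two identical columns would be conspicuous. This stands in part. The same section checks each program against its specification, so a specification that carried the SAP wording over would pass. A silent correction would leave the output at odds with the written plan.
- **The information is recoverable.** With complete wear, daytime percentage = (24 × 24-hour percentage − 6 × nocturnal percentage)/18. For the first example above, (24 × 67.5 − 6 × 60)/18 = 70%. With incomplete wear it can be recomputed from the stored readings. This stands: nothing is irreversible.
- **No endpoint definition or test depends on it.** The endpoint lists in both documents, protocol 10.4.5.1 and SAP 6.2 all describe percent time without a day/night split, and the summary is descriptive. This stands and limits the weight of the point.

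A reader might infer that daytime glycaemia, including the response to meals, would never be summarised, or that 18 hours of data are discarded. The documents do not support either reading. The 24-hour summary includes those hours at every cut point, and daytime CGM hypoglycaemic episodes are counted (SAP 4.6.4) and analysed (SAP 6.2) with the 6 a.m. to midnight window.

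**Conclusion.** The point holds as an internal contradiction in an operative rule. If programmed literally, the separate daytime percent-time summary would be a copy of the nocturnal one at every cut point, and 18 of 24 hours would be absent from both sub-period summaries. This assumes that the program follows SAP 4.6.7 to the letter; the documents do not show whether it does.

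The reach is narrow: one descriptive breakdown of a secondary endpoint. The 24-hour percent-time summary, the day/night hypoglycaemic event analyses and the primary endpoint (change in C-peptide AUC at Week 26) are unaffected. It should be corrected because the text is wrong as written and no other section sets this window, not because any conclusion of the trial depends on it.

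**What to change.** In SAP 4.6.7, change the daytime window to 6 a.m. - 12 a.m., matching SAP 4.6.3, 4.6.4 and 6.2 and protocol 10.4.5.1. Carry the change into the programming specification, and confirm there that the nocturnal and daytime windows together cover 24 hours without overlap. The cost is one phrase in the SAP. No new data, protocol change or change to any other analysis is needed.

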#### 4.6.8 Early termination (ET) visit mapping

For safety assessments, including clinical laboratory assessments, vital signs, electrocardiogram (ECG), and physical examination, the ET visit will not be mapped. The ET data will be combined

with Week 104 data for summaries, and the time point will be displayed as "Week104/ET".

For the efficacy assessment MMTT and Clark Hypoglycemia Unawareness Score, the ET visit will be mapped to the next scheduled visit at which that data type is collected. This mapped scheduled visit data will be used for analyses and summaries.

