# 2. **OBJECTIVES AND ENDPOINTS**

This first-in-human clinical trial will assess whether VC-02 can be implanted and maintained safely for up to two years in T1DM subjects with HU. During the first three to six months, VC-02 is expected to vascularize adequately, and pancreatic progenitor cells are expected to differentiate

into mature glucose-responsive, insulin-producing cells, capable of secreting insulin in response to serum glucose levels.

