### 7.2.1. 4-Hour Mixed Meal Tolerance Test

The 4-hour MMTT is conducted during Visit 2 (Week -4), Visit 11 (Week 26), Visit 13 (Week 52), Visit 15 (Week 78), and Visit 17 (Completion or ET). In addition to the time = 0 collection, samples for glucose and C-peptide are also collected at 30, 60, 90, 120, 180, and 240 minutes after the start of the Boost® meal test.

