### 7.2.2. 2-Hour Mixed Meal Tolerance Test

The 2-hour MMTT is conducted during Visit 7 (Week 8), Visit 8 (Week 12), Visit 9 (Week 16), Visit 10 (Week 20), Visit 12 (Week 39), and Visit 14 (Week 65), and Visit 16 (Week 91). In addition to the time = 0 collection, samples for glucose and C-peptide are also collected at 30, 60, 90, and 120 minutes after the start of the Boost® meal test.

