#### **13.6.1.** Handling of Withdrawals

Subjects who are withdrawn prematurely from the study will have the VC-02-300 units and sentinels explanted. If a subject withdraws from the trial and also withdraws consent for disclosure

of future information in writing, no further evaluations should be performed, and no additional data should be collected. The Sponsor may retain and continue to use any data collected before withdrawal of consent.

If a subject does not return for a scheduled visit, every effort should be made to contact the subject. It is recommended that three (3) attempts by telephone and at least three (3) attempts by certified letter should be made to contact the subject. All attempts to contact the subject must be documented in the subject's medical record. Procedures will be put in place at each site to ensure that if a subject loses contact with the trial site, alternative measures will be utilized for the collection of information. This may include contacting family members and health care providers and, when appropriate, using subject location services. In all circumstances, every effort should be made to document the subject's outcome, if possible, and to advise the subject to return to the clinic for explantation of the VC-02-300 units and sentinels.

Subjects who have not withdrawn consent, but who have been discontinued from the main study prematurely (with products explanted) will be rolled over into a long-term, follow-up trial. Those subjects may initiate any other therapy as needed to treat diabetes and any other concurrent medical conditions.

Withdrawal due to AE should be distinguished from withdrawal due to insufficient response and recorded on the appropriate AE CRF page. When a subject withdraws due to an SAE, the SAE must be reported in accordance with the reporting requirements defined in Section 8. The reason for discontinuation will be documented in the subject's source records.

For safety reasons, all early termination procedures (including explantation procedure) as described in Visit 17/ET and Visit 18 should be performed if a subject discontinues the trial.

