#### 4.3 Assessment Windows

For the purpose of analyzing time to event endpoints, the time-in-study for each subject will be measured relative to Day 1, the day that the surgical procedure for VC-02-300 and/or sentinel unit implantation was attempted.

Study Visit	Target Study Day of Visit	SAP Windows		
Scheduled Study Visits for Cohort 1 and Cohort 2				
Week -4	-29	Day -36 to Day -23		
Week -3	-22	Day -22 to Day -1		
Day 1	1	Day 1		
Day 2	2	Day 2 to Day 3		
Week 2	15	Day 4 to Day 21		
Week 4	29	Day 22 to Day 42		
Week 8	57	Day 43 to Day 70		
Week 12	85	Day 71 to Day 98		
Week 16 (Cohort 1 Only)	113	Day 99 to Day 117		
Week 16 (Cohort 2 Only)	113	Day 99 to Day 126		
Week 17 (Follow-Up		Day 118 to Day 118+		
Visit: Cohort 1 Only)	120			
	Scheduled Study Visits for Col	nort 2 Only		
Week 20	141	Day 127 to Day 161		
Week 26	183	Day 162 to Day 228		
Week 39	274	Day 229 to Day 319		
Week 52	365	Day 320 to Day 410		
Week 65	456	Day 411 to Day 501		
Week 78	547	Day 502 to Day 592		
Week 91	638	Day 593 to Day 683		
Week 104	729	Day 684 to ∞		
Week 105 (Follow-Up Visit)	Last Date of Explantation + 7 Days	Not applicable		

Study visits will have windows as per the following schema:

The data will be summarized based on the electronic case report form (eCRF) (Study Visit) in which it was collected as long as the data is within the windows specified. If data for a particular Study Visit is not within the windows specified, then queries will be sent to the site to confirm data entry. ViaCyte will be notified of Study Visits that are not within the Study Visit Statistical Analysis Plan (SAP) windows. Data collected as an unscheduled visit will be re-assigned to a Study Visit based on the SAP visit windows specified.

Baseline will be defined as the last non-missing value prior to the start time of the surgical procedure for VC-02-300 and/or sentinel unit implantation, unless otherwise specified.

If more than one assessment exists within a single visit window (i.e., vital signs, laboratory samples, etc.), then the value taken closest to the target day of that visit will be used for analysis and summary purposes. In cases where two assessments are equally close to the target day, then

the first value will be used for analysis. Data from all assessments will be provided in the listing.

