#### 4.6.1 C-peptide AUC0-4h and AUC0-2h

Area under the curve (AUC) is calculated by adding the areas under the curve between each pair of consecutive observations. The calculation is based on the trapezoidal rule:

$$AUC = \frac{1}{2} \int_{i=1}^{n-1} (t_{i+1} - t_i) (y_i + y_{i+1})$$

Where there are n C-peptide measurements  $y_i$  at nominal time points  $t_i$  (i=0,...,n-1), and  $(t_i+1-t_i)$  will be measured in hours.

Specifically,

$$\begin{aligned} AUC_{0-4h} &= 0.5(y_0 + y_{0.5})/2 + 0.5(y_{0.5} + y_1)/2 + 0.5(y_1 + y_{1.5})/2 + 0.5(y_{1.5} + y_2)/2 \\ &+ 1(y_2 + y_3)/2 + 1(y_3 + y_4)/2 \end{aligned}$$

$$AUC_{0-2h} = 0.5(y_0 + y_{0.5})/2 + 0.5(y_{0.5} + y_1)/2 + 0.5(y_1 + y_{1.5})/2 + 0.5(y_{1.5} + y_2)/2$$

After Implantation Visit 3, 2-hour MMTTs will be conducted at Visit 7 (Week 8), Visit 8 (Week 12), Visit 9 (Week 16), Visit 10 (Week 20), Visit 12 (Week 39), Visit 14 (Week 65), and Visit 16 (Week 91). After Implantation Visit 3, 4-hour MMTTs will be conducted at Visit 11 (Week 26), Visit 13 (Week 52), Visit 15 (Week 78) and Visit 17 (Week 104 or Early Termination). For subjects with an immeasurable C-peptide ( $\leq 0.1$  ng/mL) as determined by the simplified oral glucose challenge test, the AUC of the respective 2-hour MMTT will be set to 0. C-peptide results reported as  $\leq 0.1$  ng/mL will be imputed as 0 for determination of the AUC0-4h and AUC0-2h.

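### SAP 4.6.8 moves early-termination MMTT and Clarke values forward to the next scheduled visit with no limit on the gap, so values taken before explantation can be analysed outside the SAP's own visit windows.

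*SAP*

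**What the plan says.** SAP 4.6.8 treats ET data in two ways. Safety data are not mapped and are pooled with Week 104. For the MMTT and the Clarke score, "the ET visit will be mapped to the next scheduled visit at which that data type is collected", and "This mapped scheduled visit data will be used for analyses and summaries". No maximum gap is given.

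SAP 4.3 has a different rule for other off-schedule data: "Data collected as an unscheduled visit will be re-assigned to a Study Visit based on the SAP visit windows specified". SAP 4.6.8 does not refer to those windows.

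The MMTT done at ET is the 4-hour test. SAP 4.6.1 places the post-implant 4-hour tests at "Visit 11 (Week 26), Visit 13 (Week 52), Visit 15 (Week 78) and Visit 17 (Week 104 or Early Termination". The other MMTTs are shorter. Protocol 7.2.2 states: "The 2-hour MMTT is conducted during Visit 7 (Week 8), Visit 8 (Week 12), Visit 9 (Week 16), Visit 10 (Week 20", and continues with Weeks 39, 65 and 91. The Clarke survey is given after implant at Weeks 16, 26, 39, 52, 78 and 104 (Protocol 7.12).

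When a subject leaves early, "all early termination procedures (including explantation procedure) as described in Visit 17/ET and Visit 18 should be performed" (Protocol 13.6.1). Protocol 7.2 allows the MMTT to precede an explant by up to 5 days.

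**The concern.** Visit-based analysis of an implant assumes that a Week 26 value comes from a graft of about 26 weeks. Protocol section 2 shows why age matters: "During the first three to six months, VC-02 is expected to vascularize adequately", and the cells are expected to mature over the same period. The mapping rule separates the visit label from graft age. It also assigns a result obtained with the graft in place to a later date, when the graft is gone.

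The estimates at stake are the Week 26 change in C-peptide AUC0-4h, which is the Cohort 2 primary endpoint and feeds the review before a possible End-of-Phase 2 meeting (SAP 9.1), and the later AUC and Clarke analyses. The 9-12 month risk/benefit assessment (Protocol 10.3.2) can end participation for Cohort 2 subjects, so exits in that period are foreseen by the plan. SAP 4.4 has no other rule for missing visits, and no sensitivity analysis of mapped values is planned.

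**Working it through.** **Inputs.** Target days and windows are from SAP 4.3 (Cohort 2), MMTT visits from SAP 4.6.1 and Protocol 7.2, and Clarke visits from Protocol 7.12. I assume that scheduled visits fall on their target days and that the ET assessment is dated on the ET day.

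**1. Reproduce the SAP windows.** Target day = 7 × week + 1, so Week 26 = 183, Week 39 = 274 and Week 52 = 365. Window limits are midpoints between neighbouring targets: (141 + 183)/2 = 162 and (183 + 274)/2 = 228.5. This gives Day 162-228 for Week 26, as stated. In the same way Week 52 is Day 320-410.

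**2. Map each possible ET day to the next visit.** Shift = target day − ET day.

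| Reading | ET days | Mapped to | Days outside that visit's window | Maximum shift |
|---|---|---|---|---|
| 4-hour MMTT only | 2-182 (181 days) | Week 26 | 160 (88%) | 181 days = 25.9 weeks |
| 4-hour MMTT only | 184-364 (181) | Week 52 | 136 (75%) | 25.9 weeks |
| 4-hour MMTT only | 366-546 and 548-728 (181 each) | Weeks 78 and 104 | 136 (75%) each | 25.9 weeks |
| Any MMTT | 142-182 (41) | Week 26 | 20 (49%) | 41 days = 5.9 weeks |
| Any MMTT | 275-364 (90) | Week 52 | 45 (50%) | 12.9 weeks |
| Clarke | 2-112 (111) | Week 16 | 97 (87%) | 15.9 weeks |
| Clarke | 114-182 (69) | Week 26 | 48 (70%) | 9.9 weeks |
| Clarke | 184-273 and 275-364 (90 each) | Weeks 39 and 52 | 45 (50%) each | 12.9 weeks |
| Clarke | 366-546 and 548-728 (181 each) | Weeks 78 and 104 | 136 (75%) each | 25.9 weeks |

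For the first row, the days inside the window are 162-182, which is 21, and 181 − 21 = 160. These are shares of possible days, not of expected subjects.

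**3. What holds under both MMTT readings.** An ET on Day 275-319 goes to Week 52. The shift is 365 − 319 = 46 days to 365 − 275 = 90 days, and every one of these days is before Day 320. They fall in the 9-12 month period.

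**4. Does the MMTT waiver remove this?** After a risk/benefit exit, the ET 4-hour MMTT need not be repeated if one was done within 8 weeks (Protocol 10.3.2). The last scheduled 4-hour test before Week 52 is on Day 183, since Week 39 is a 2-hour test. On schedule the waiver therefore ends at 183 + 56 = Day 239 and does not reach Day 275-319. After Week 52 it runs to 365 + 56 = Day 421, so such exits may have no ET MMTT to map. The waiver's examples are the MMTT and the safety ultrasound, not the Clarke survey.

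**5. The opposite error.** An ET on Day 184-228 is inside the Week 26 window, but it is sent to Week 39 (any MMTT) or Week 52 (4-hour only).

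**6. Illustration of size.** The documents give no ET count. Assume 40 subjects, k ETs mapped into Week 26, f = k/40, and an ET response equal to a fraction r (0 to 0.5) of the mature response.
- Mapped mean relative to the mature-graft mean: 1 − f(1 − r).
- Mapped mean relative to a target in which a removed graft counts as zero: [(1 − f) + f·r]/(1 − f).

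| k | Relative to mature graft | Relative to removed graft = 0 |
|---|---|---|
| 2 | 95-97.5% | 100-102.6% |
| 4 | 90-95% | 100-105.6% |
| 8 | 80-90% | 100-112.5% |

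The same mapping lies below one target and at or above the other.

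**The case against.** The any-MMTT reading is arguably the more natural one. SAP 4.6.8 says MMTT without a length, and SAP 4.6.1 takes the 2-hour baseline from the first two hours of the 4-hour test. On that reading a Week 5 exit goes to Week 8, and only Days 142-182 reach the primary analysis, 21 of them already inside the window. This stands. A reader might infer that every exit before Week 26 supplies a primary value, but that follows only if the data type is the 4-hour test. The SAP leaves this open, so two programmers could build different Week 26 datasets.

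A reader might also infer that the rule overstates durability. The documents do not support a fixed direction. C-peptide is one factor in the risk/benefit assessment, so subjects removed for poor function may carry low values forward, which would lower later means compared with leaving them out. Upward bias requires a target in which a removed graft counts as lost, and the plan states no such target.

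Forward mapping is pre-specified and keeps early exits in a set the SAP calls intent-to-treat. Dropping those values with nothing in their place would favour completers. This also stands and shapes the fix.

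Finally, no hypotheses are tested, and the planned listings make mapped values traceable. That limits the harm. The visit estimates are still affected.

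**Conclusion.** The concern holds. Followed as written, SAP 4.6.8 places out-of-window values in the visit analyses under either reading of data type. For the primary endpoint the exposure runs from 20 of 41 possible ET days (shift up to 41 days) to 160 of 181 (shift up to 25.9 weeks). For Week 52, Days 275-319 are affected in both cases. Clarke values move up to 25.9 weeks and reach Weeks 16 and 39 as well as Weeks 26, 52, 78 and 104.

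Three limits apply. Not every mapped value is misplaced: an ET on Day 162-182 belongs in Week 26 under SAP 4.3. Not every exit after the risk/benefit assessment is affected, because the waiver may remove the ET MMTT soon after Week 52. The consequence is a biased or mislabelled visit estimate of unknown direction, not an inflated error rate.

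The day counts assume visits on their target days. The size of the effect depends on the number of ETs and their responses, which the documents do not give.

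**What to change.** Replace the efficacy rule in SAP 4.6.8 with the following.

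- Assign ET MMTT and Clarke data to the SAP 4.3 window that contains the actual ET study day.
- Use AUC0-4h at Weeks 26, 52, 78 or 104 only if the day is in that visit's window.
- Allow AUC0-2h from the same test to serve a 2-hour visit whose window contains the day. An ET on Day 275-319, for example, falls in the Week 39 window.
- Show values that fit no applicable window as ET in the listings.

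No separate bar on pre-explant values is needed, because the window governs. An ET on Day 170 is 13 days before the Week 26 target and properly counts there. Under this rule an ET value used at Week 26 is at most 21 days early (183 − 162) or 45 days late (228 − 183).

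The change leaves fewer values and could favour completers, so add two sensitivity analyses of the Week 26 and later AUC endpoints:

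- (a) with forward-mapped ET values, after stating which MMTTs count as the same data type;
- (b) with post-explant C-peptide AUC set to zero.

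The cost is SAP wording, one changed programming rule, two additional analyses and fewer values at scheduled visits. No new data are needed.
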